9.2 Baseline Visit

9.2.1 Pre-operative enrolment

Enrolment of eligible patients might be performed at a patient's visit in hospital up to 3 months prior to thyroid surgery. In any case, prior to any data documentation in e-CRF and prior to any trial related procedure, a signed informed consent form has to be obtained from every patient to be enrolled in HEDOS and kept on

file locally. The date of written informed consent will be documented in e-CRF (= date of enrolment), even if weeks prior to thyroid surgery. It represents day 1 of the study participation of each individual patient.

The date of the baseline visit is the date of documenting in- and exclusion criteria (= screening process). Other clinical assessments may also be documented on this date even if their date of origin is prior to baseline visit but within the permitted time window. The date of the baseline visit must not be prior to the date of enrolment.

At the baseline visit, the investigator or designee will:

- Obtain patients' informed consent (investigator, may be prior to baseline visit) and document it (investigator or designee).
- Document all inclusion and exclusion criteria.
- Assess patient's medical history.
- Perform physical examination, record vital signs and document routine clinical laboratory parameters.
- Document concomitant medication.
- Document index thyroid surgery including placement of sensor(s) and data on IP used.
- Document and assess any adverse event from enrolment until hospital discharge.
- Ask the patient to complete the EQ-5D-5L and the GAD-7 questionnaires prior to thyroid surgery.

A patient meets eligibility criteria of the study if he passed all inclusion and exclusion criteria as described in the sections above.

9.2.2 Thyroid surgery

Index thyroid surgery should preferably be performed during the same hospital stay as the baseline visit. However, if a patient provided signed informed consent at an outpatient visit prior to the index thyroid surgery stay, mandatory data obtained at both patient visits will be documented in the baseline visit.

Index thyroid surgery should in any case be performed within 3 months after the patient gave informed consent for study participation (= date of enrolment).

Any event during the hospital stay for index thyroid surgery which fulfils criteria of an adverse event has to be adequately documented in the eCRF.

The baseline visit ends with hospital discharge.

9.3 Follow-up

The day of index thyroid surgery is day 1 of follow-up on primary and secondary endpoints.

Each patient will be followed until one month after day of index thyroid surgery (\pm 7 days related to visit schedules as displayed in the e-CRF) or until withdrawal of consent (WOC) or death.

9.3.1 Clinical follow-up after 1 month using patient questionnaires

One month after day of index thyroid surgery (± 7 days related to visit schedules as displayed in the e-CRF) or triggered by documentation of withdrawal of consent (WOC), three questionnaires will be sent to the patients by their corresponding study sites together with toll-free envelopes for reply. Patients will be asked to:

- Complete the EQ-5D-5L and the GAD-7 questionnaires
- Document clinical events in a FU questionnaire which are suspicious as AEs.

In case of missing reply after one written reminder by the study site, the patient will be contacted by the study site by phone in order to obtain the required information.

In case a patient reports a clinical event, which is suspicious as SAE, the responsible study site will contact the patient's family doctor, and / or the hospital where the patient was treated, and ask for supporting documents (i.e. hospital discharge letter, diagnostic reports) as applicable. The study site is responsible for completion of the reported event data in the e-CRF.

9.4 Patient Withdrawal from the Study

Individual study participation is only prematurely terminated in case of patient's death or explicit wish (withdrawal of consent). Premature termination of study participation of a study patient is not possible by decision of an investigator.

If a patient expresses his **Withdrawal Of Consent (WOC)** to any further study participation, completion of FU documentation in e-CRF is mandatory. If WOC is expressed during a personal site visit, site staff should document AEs since last assessment, ask the patient to complete the EQ-5D-5L and the GAD-7 questionnaires and send them to CRI. If withdrawal of consent is expressed not during a personal site visit, site staff should inform the patient that final questionnaires will subsequently be send to him by mail and should ask the patient to complete and send them to CRI.

9.5 Blood Samples

Routine laboratory parameters obtained within routine clinical care are part of the standard work-up of the patient's status before study participation and therefore not considered as part of study related procedures. If these parameters can be assessed from a blood sample not older than 14 days at the date of baseline visit, blood sampling and analysis do not have to be repeated within the study baseline visit.

All blood parameters will be determined at local laboratory provided their analytical laboratories are certified. In the e-CRF laboratory values and information whether the value is assumed to be clinically normal or abnormal will be documented. Standard normal values of the corresponding laboratory will not be documented because the assessment of clinical abnormality is more relevant in this trial compared to formal rating against normal values (e.g. in case of chronic diseases).

10. Duration of Study Participation

The following definitions apply only to the diagnostic accuracy study HEDOS, that for HEDOS II will be defined in the corresponding study protocol.

10.1 Overall Duration of the Study

Enrolment of patients is expected to be accomplished after about 12 months. Last Follow-up assessment will be reached about 1 month after enrolment of the last patient. Thus, total study duration of about 12 months + 1 month = 13 months plus 1 month for final data cleaning is expected. The total study duration is expected to be about 14 months.

Global end of study (EOS) is defined as the date of the last clinical follow-up on outcome after 1 month performed in a study patient (= last patient last visit). This date will be approved by the sponsor and announced to the sites by the CRO.

10.2 Individual Duration of the Study

The follow-up time for each patient will be about 1 month. Every patient will be followed according to study protocol until about one month after index thyroid surgery, withdrawal of consent or death.

11. Stopping and Discontinuation Criteria

When the study is terminated, the nature of termination will be documented (scheduled end/premature termination with justification). Termination of the study will be communicated in writing according to the legal requirement, premature termination in line with rules for expedited reporting. The decision to stop the study will be reached jointly by sponsor and SC.

11.1 Discontinuation Criteria related to the Study

Following a recommendation of the SC, the sponsor may decide discontinuation of the study due to efficacy criteria or safety concerns. Discontinuation of the study can also be decided if patients cannot be recruited in sufficient numbers within a certain time period.

Furthermore, the sponsor in collaboration with the Chief Investigator (CI) has the right to close local study sites for enrolment of further patients if major protocol deviations occur, if the site does in general not adequately comply with the study protocol or decisions of the committees or the CI or if the site remains inactive for several months. Such decisions will always be taken on a case-by-case basis.

11.2 Discontinuation Criteria related to the Patient

- The investigator is not able to decide about the discontinuation of study participation of any patient enrolled. In this case, after enrolment and index thyroid surgery the patient will continue to be followed according to study protocol until about 1 month after index thyroid surgery, withdrawal of consent or death.
- Study patients will be advised in the informed consent forms that they have the right to withdraw from study participation at any time without giving reasons. However, the investigator should try to find out the reason for patient's withdrawal of consent and document it in the e-CRF.
- In case that a protocol deviation is noticed, the patient will stay in the trial and will be followed according to protocol.
- In case that an AE/SAE occurs which is not death, the patient will stay in the trial and will be followed according to protocol.

Reasonable effort should be made to contact any patient lost to follow-up during the course of the study in order to complete assessments and retrieve any outstanding data. The responsible investigator will take all acceptable measures to retrieve information on outcome of all patients enrolled in the trial.

12. Statistics and Methods

A general description of the statistical methods to be used to analyse the diagnostic accuracy study (stage 1 of the seamless design) is outlined below. The subsequent stage 2 study of the seamless design will be described in detail in a separate study protocol with reference to this document, to be finalised after the results of the first study are available. A more detailed statistical analysis plan (SAP) is provided in a separate document for both stages together.

Statistical analyses will be performed using SAS and R, the version used will be specified in the SAP. The SAP will accommodate protocol amendments or unexpected issues in study execution or data that affect planned analyses, and will provide more details on the analytic approaches, coding guidelines, censoring of time-to-event variables, and output tables and figures.

12.1 Statistical Methods

12.1.1 Description of Baseline characteristics

A descriptive analysis of parameters assessed at baseline will be performed. Categorical variables are summarised by absolute and relative frequencies. Continuous variables are summarised by mean and standard deviation (SD) or by median, quartiles and/or interquartile range (IQR), as appropriate. The number of available observations and the number of missing observations are reported separately for the diagnostic groups (clinically relevant hemorrhage present vs. not present).

12.1.2 Analysis of the primary endpoint

Analyses of the co-primary endpoints in the stage 1 diagnostic study are based on the population of all enrolled patients with subsequent index thyroid surgery. This corresponds to the intention to diagnose (ITD) principle, whereas missing or inconclusive values are imputed by false positive or false negative results, respectively [25]. In accordance with the ICH E9 guidelines, the analysis population of all these patients is defined as the "Full Analysis Set" (FAS).

In the first pair of primary hypotheses, sensitivity and specificity are considered as co-primary endpoints. They are combined via the Intersection-Union Test. The global null hypothesis can only be rejected if both individual null hypotheses of sensitivity and specificity are rejected. The corresponding first global alternative hypothesis states that the IP exceeds a pre-defined minimum sensitivity of 80% and specificity of 65%. The second primary global hypotheses, the second primary global hypothesis can only be evaluated in a confirmative way if the first global primary hypothesis leads to a significant result. The hierarchical order of hypotheses requires no adjustment of the type I error rate.

The analysis of the first global primary hypothesis contains the estimation of the resulting sensitivity and specificity of the IP according to the defined cut-off value of 12 mmHg. For the estimation, a mixed binary logistic regression model is used [26]: The binary test result represents the dependent variable, the true disease status is included as fixed effect. Additionally, a random-intercept is estimated for each centre. Sensitivity is estimated via the calculation of the marginal mean for a diseased individual (=surgical intervention performed which confirmed post-operative hemorrhage needing intervention). False-positive rate, which is the counter probability of the specificity, is estimated via the calculation of the marginal mean for a non-diseased individual. Twosided 95%-logit confidence intervals with p-values are reported.

If the mixed binary logistic regression model does not converge, a non-parametric multi-factorial approach is used to estimate sensitivity and specificity [27]. With this approach, separate estimates of sensitivity and specificity, respectively, are calculated for each centre and finally weighted averaged. Two-sided 95%-logit confidence intervals for the averaged sensitivity and specificity and p-values based on Analysis-of-Variance-type-statistics are reported.

The first primary null hypothesis can be rejected if the lower limit of both confidence intervals lies above the according pre-defined minimum threshold (0.8 for sensitivity and 0.65 for specificity).

The analysis of the third primary endpoint regarding the area under the receiver-operating characteristic curve (AUC) of the three-level decision rule is performed in analogy to the analysis of the first co-primary pair. The according null hypothesis can be rejected if the lower limit of the confidence interval lies above the according pre-defined minimum threshold of 0.7.

Further details will be specified in the SAP.

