3.3 Benefit-risk Assessment

3.3.1 General risk assessment of the HEDOS trial

- The study is purely diagnostic without any pre-defined therapeutic intervention in the study protocol. No random assignment to therapies is performed in this one-arm diagnostic accuracy trial.
- The indication for thyroid surgery and the consent of the patient to this therapeutic approach are decided in routine clinical care prior to any HEDOS trial activities in the corresponding patient.
- All medical therapies are at the discretion of the treating physician according to applicable medical guidelines and local treatment policies. Treatments and procedures will be decided by the treating physician based on the individual medical status of each study patient without guidance by the study protocol.
- All medical devices with the exception of the IP diagnostic device and drugs which may be used within
 the study will be marketed products to be used in line with market authorisation as given in their Instruction For Use (IFU) or Summary of Product Characteristics (SmPC) and represent standard of care
 (SOC). This also applies to the medical procedures within the trial. Thus, adverse events resulting from
 therapies within the study are expected to occur in similar clinical manifestations and at comparable
 rates as the known adverse events of the approved therapies in routine clinical care.
- The IP is only used as an external small box fixed at the upper arm of the patient by a soft silicone bracelet. A sterile disposable compartment pressure probe is placed in the surgical area at the end of the routine thyroid surgical procedure just before wound closure and subsequently connected to the device (in case of surgery on both sides two pressure sensors have to be used but both connected to just one external device box). Potential risks of this equipment are local infections at the suture or in the surgical area comparable to the risks of wound drainage often used after thyroid surgical procedures in routine

clinical care. However, pressure sensor catheter and the suture are protected by adequate dressing and the sensor will be removed completely within 48 hours after wound closure without reopening the suture.

- The measurements of the IP are kept secret until the end of the trial and, therefore, do not affect treatment decisions.

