6.2 Study Population

6.2.1 Number of patients and definition of status

HEDOS will enrol and measure presumably 1,470 eligible adult patients and follow each of them for 1 month, assuming that 22 events of clinically relevant hemorrhage within 48 hours following thyroid surgery will be observed.

A patient is considered as enrolled into the trial according to regulatory requirements as soon as he has **signed** the informed consent form. Documentation of any patient data in the e-CRF is permitted only after the patient signs the informed consent form. All enrolled patients will be reported and will be part of the safety population. Enrolled patients who are subsequently not measured with thyroid surgery as defined in the study protocol will not count to the number of enrolled patients needed, and will be replaced as soon as absence of thyroid surgery has been determined and documented in the clinical files of the patient.

A patient is considered as **screened** as soon as inclusion and exclusion and other eligibility criteria have been checked and documented in the e-CRF after the patient signed the informed consent form. Screened patients who are subsequently not measured with thyroid surgery as defined in the study protocol will not count to the number of enrolled patients needed, and will be replaced as soon as absence of thyroid surgery has been determined and documented in the clinical files of the patient. These patients will be followed until date of determination of absence of thyroid surgery. If a screened patient is scheduled for index thyroid surgery after global end of the study or after termination of study participation of the corresponding study site his study participation will end at the corresponding date of administrative termination. A patient is considered as measured in the trial as soon as he is **enrolled and thyroid surgery** as defined in the study protocol was performed. All measured patients will be part of the ITD population. Measured patients will be followed according to study protocol.

The day of **enrolment** is **day 1 of study participation**, the **day of index thyroid surgery** as defined in the study protocol is **day 1 of follow-up** for primary and secondary endpoints of an individual study patient.

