6.2.4 Randomisation (Rx)

For this type of purely diagnostic trials no randomisation (Rx) into treatment groups is required (within-subject design). All patients passing in- and exclusion criteria and subsequent index thyroid surgery will receive the diagnostic IP and will be assessed.

7. Therapy

Within this purely diagnostic trial by study protocol no medical treatment is defined other than thyroid surgery as inclusion criterion. Indication for thyroid surgery, type of surgery performed (e.g. total thyroidectomy, sub-total resection, partial resection or lobectomy) and procedures before, during and after surgery are at the discretion of the treating physician in routine clinical care according to applicable medical guidelines and local policies, and are not defined in the study protocol. Therapies provided to study patients will be documented as required in the e-CRF.

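### The protocol defines 'measured' and the full analysis set in two incompatible ways (6.2.1 and 12.1.2 against 12.4); with about 22 bleeds, the choice between them can decide the sensitivity test

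*Protocol*

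**What the plan says.** **The wide definition.** Protocol 12.1.2 (repeated in the synopsis) says the co-primary analysis is "based on the population of all enrolled patients with subsequent index thyroid surgery". It names this set the FAS and adds that "missing or inconclusive values are imputed by false positive or false negative results, respectively". I read this as false positive for a patient without a bleed and false negative for a patient with one.

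Section 6.2.1 supplies the terms. A patient is enrolled "into the trial according to regulatory requirements as soon as he has" signed consent. Screening comes next, when "eligibility criteria have been checked and documented in the e-CRF after the patient signed the informed consent form". 'Measured' means enrolled and operated. Then: "All measured patients will be part of the ITD population". The only ground for replacement is that surgery did not take place.

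**Who gets the device.** Section 6.2.4: "All patients passing in- and exclusion criteria and subsequent index thyroid surgery will receive the diagnostic IP and will be assessed". The single exclusion criterion, E1, is a planned drain.

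**The narrow definition.** Section 12.4 says a patient is 'measured' once enrolled, screened and operated, and once pressure monitoring with the device has begun. It makes these patients the FAS, then refers to 6.2.1 for details, which is the text it conflicts with.

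**The concern.** The same two terms, 'measured' and FAS, select different patients for the primary test.

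- *Consented, found to need a drain (E1), operated without a probe.* In under 6.2.1 and 12.1.2, with an imputed error. Out under 12.4.
- *Eligible, operated, probe not placed or monitoring never begun.* In and imputed under 6.2.1 and 12.1.2. Out under 12.4.

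Intention-to-diagnose should count against the device its failures in patients in whom it was meant to be used. The wide definition goes further and counts patients from whom the plan itself withheld the device. The narrow one stops short and removes real failures. Neither uses eligibility as the dividing line: 'screened' in 12.4 means that the criteria were checked, not that they were met.

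The first kind of patient can occur. E1 does not cancel an operation that is already indicated, and consent may precede surgery by up to three months (9.2.1). Section 3.3.1 describes the probe's risks as "comparable to the risks of wound drainage often used after thyroid surgical procedures in routine" care, so drains are not rare in this surgery. That sentence concerns thyroid surgery in general, however, and gives no rate for consented trial patients.

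'Measured' also governs the count of 1,470 and the half-way point at which prevalence is re-estimated (12.3), so the ambiguity reaches the sample size as well.

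**Working it through.** **Inputs (protocol 12.2 and 12.1.2).** Assumed sensitivity 0.99, minimum 0.80; assumed specificity 0.95, minimum 0.65; prevalence 1.5%; two-sided 5%; N = 1,470; 22 bleeds; stated power for sensitivity 86%. Success requires a lower 95% limit above the minimum.

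**Step 1: reproduce the plan.** 1,470 × 0.015 = 22.05 bleeds. With n = 22:

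power = Φ{[(p1 − 0.80) − 1.96·√(0.80·0.20/n)] / √(p1(1 − p1)/n)}

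At p1 = 0.99 this is Φ[(0.19 − 0.1672)/0.0212] = 0.859, matching the stated 86%.

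**Step 2: one patient without a reading.** Suppose 22 consented, operated patients bleed. The device detects 21, and one has no recording.

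- Patient kept and imputed: 21/22 = 0.955. The lower 95% limit is 0.739 (simple logit), 0.772 (Clopper-Pearson) or 0.782 (Wilson). All lie below 0.80, so the test fails.
- Patient dropped: 21/21. The Clopper-Pearson lower limit is 0.025^(1/21) = 0.839; Wilson gives 21/(21 + 1.96²) = 0.845. Both lie above 0.80, so the test succeeds.

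The same data give opposite conclusions, depending on which section is followed.

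**Step 3: conditional loss of power.** Let s be the share of analysed patients who have no reading and are imputed. The protocol gives no value, so s is an assumption, as is a bleed rate equal to that of the other patients. Expected sensitivity is then 0.99(1 − s), entered as p1 in the Step 1 formula. The chance that at least one of 22 bleeds falls in such a patient is 1 − (1 − s)^22.

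| s | patients (of 1,470) | expected sensitivity | power | chance of ≥1 such bleed |
|---|---|---|---|---|
| 0 | 0 | 0.990 | 86% | 0 |
| 1% | 15 | 0.980 | 67% | 20% |
| 2% | 29 | 0.970 | 53% | 36% |
| 5% | 74 | 0.941 | 30% | 68% |
| 10% | 147 | 0.891 | 13% | 90% |

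The expected estimate reaches 0.80 when 1 − s = 0.80/0.99 = 0.808, that is, s of about 19%.

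An exact binomial test, which needs 22 of 22, gives 80%, 64%, 51%, 26% and 8% for the same rows.

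**Step 4: specificity.** 0.95(1 − s) is 0.9025 at s = 5% and 0.855 at 10%. The reported value falls, but with about 1,448 patients without a bleed the test against 0.65 is not in danger at these shares.

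**The case against.** A reader of 12.1.2 and 6.2.1 alone might infer that the protocol has settled on imputing screen failures as device errors, and that this drags sensitivity under its threshold. The documents do not support that reading.

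- Section 12.4 is the section on selecting patients for analysis. It would keep anyone without monitoring out of the FAS.
- Section 6.2.1 opens by planning for 1,470 *eligible* patients, so the intended count is probably of eligible patients only.
- Section 6.1 describes pre-screening from routine data before inclusion. Many planned drains would be known before consent, and the remaining cases may be few.
- The rule in 9.4, "Premature termination of study participation of a study patient is not possible by decision of an investigator", concerns participation and follow-up. It does not decide analysis sets.
- The power figures rest on an assumed s. The formula is the one that matches the planning figure, not the planned analysis, which takes logit intervals from a mixed model. Baseline power depends strongly on method: 86% as planned, 80% exact, 32% by a simple logit-scale approximation.

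All of this stands, and it limits the point to a contradiction. It does not remove it. Section 12.4 does not say that it overrides 12.1.2, and both claim the label FAS. The qualifier in 6.2.1 that surgery be as the protocol defines it filters nobody, because section 7 leaves the operation to routine care. Nor would adopting 12.4 be a neutral repair, since it drops eligible patients in whom the device failed at the outset. A statistical analysis plan, not available here, could add detail, but it would have to depart from one of the two protocol definitions.

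**Conclusion.** The point holds as an internal contradiction in the primary analysis set, with each version wrong in a different direction. That one patient can reverse the sensitivity conclusion follows from the planned 22 bleeds and the 0.80 limit, and needs no assumption about s. It does use simple one-sample intervals in place of the mixed model.

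The loss of power (to 67%, 53% or 30% at s = 1%, 2% or 5%) is an illustration that depends on an unknown s and on equal bleed rates. It is not a forecast. It is not shown that sensitivity would be pulled below its minimum: that would need about 19% of analysed patients without a reading. Specificity is affected in its reported value, not in its test. The definition should be corrected before the primary analysis set is fixed.

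**What to change.** Use one definition in 6.2.1, 12.1.2, 12.4 and the synopsis:

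- **ITD/FAS:** all enrolled patients who were documented before surgery, independently of any pressure reading, as meeting every inclusion and exclusion criterion, and who had index thyroid surgery, whether or not the probe was placed or monitoring began. Keep the worst-case imputation for these patients.
- **12.4:** delete the condition that monitoring has begun from the FAS definition.
- **Screen failures:** patients who fail eligibility at screening are not 'measured', are not counted in the 1,470 or in the interim prevalence, are replaced, and are listed with the reason.

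**Cost.** Wording in four places; eligibility is already recorded in the e-CRF. The record must be locked before surgery, so that difficult cases cannot be relabelled afterwards, and some consented patients will have to be replaced. Eligible patients without monitoring will count against the device. The Step 3 table shows the price if s is read as their share, so the assumed 99% sensitivity has to be understood as including them.

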HEDOS represents stage 1 of the seamless design and is planned as a prospective, single-arm, multi-centre, blinded, observational, diagnostic accuracy study with a diagnostic medical product. The occurrence of a post-operative hemorrhage with need for intervention, detected in routine clinical care, is considered as gold standard. It will be conducted in Germany and Austria with about 50 clinical sites participating. The study has a planned number of n=1,470 enrolled and measured patients within a follow-up period of 1 month after end of index thyroid surgical procedure. It is expected to observe about 22 cases of clinically relevant hemorrhage within 48 hours following thyroid surgery within the trial.

It is expected that patient recruitment is completed after about 12 months from the time the first patient is enrolled. The clinical phase of the trial will end about 1 month after the last patient has been enrolled and measured.

Further, a blinded sample size re-calculation based on the incidence of bleeding events measured by the gold standard procedure within the stage 1 study is planned (see section 12.3 for further details).

The randomized test-treatment study in stage 2 will be planned as a multi-center, confirmatory, prospective, parallel-group phase IV diagnostic cluster randomized test-treatment trial comparing the effectiveness of the IP detector vs. routine clinical care monitoring in a consecutive sample of patients undergoing a thyroid surgery. In the first step, all study sites will be randomized to either apply the IP detector (intervention group) on patients undergoing thyroid surgery or to perform routine clinical care monitoring (control group).

Hereby, the control group information is augmented with information coming from the phase III trial in stage 1 [21, 22, 23]. Since these patients are monitored in a routine clinical way and further receive treatment according to current routine clinical care standards anyway, serious heterogeneity with the control arm of the stage 2 study is not expected. Thus, the focus of patient enrolment will mainly be on recruiting study sites and their eligible patients into the intervention group.

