12.2 Sample Size and Power Calculations

Initial sample size calculation for the stage 1 study is performed for the first primary hypothesis considering sensitivity and specificity as co-primary endpoints. This hypothesis states the superiority considering sensitivity and specificity of the IP against pre-defined minimum thresholds. The optimal sample size calculation for a single-arm confirmatory diagnostic accuracy study is applied [28].

The sensitivity of the IP is assumed to be 99%, the specificity is assumed to be 95%. The pre-defined minimum sensitivity equals 80%, the minimum specificity is 65%. A higher minimum sensitivity than minimum specificity is chosen as false negative results are much more relevant for the patient than false positive results. The assumed prevalence of clinically relevant hemorrhage within 48 hours following thyroid surgery is 1.5%. The two-sided significance level is set to 5% for the endpoint considering sensitivity and the endpoint considering specificity, respectively. An overall power of 80% is aimed. This leads to a total sample size of 1,470 patients enrolled and measured which is based on the assumed prevalence of 1.5%. Due to the optimal sample size calculation, the endpoint considering the sensitivity reaches a power of 86% and the endpoint considering the specificity a power of 98%. If the prevalence differs at least 22 events of clinically relevant hemorrhage within 48 hours following thyroid surgery need to be observed. Consecutive patient recruitment without any selection is important to receive valid estimates of predictive values as secondary endpoints.

The sample size calculations are performed with R version 4.0.2.

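### The logit-interval rule for sensitivity is not the test behind the stated 86% power, and at the planned 22 bleeds it has very little power

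*Protocol*

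**What the plan says.** Section 12.1.2 of the protocol fixes four elements of the confirmatory test of sensitivity.

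- **Model:** binary test result on true disease status, with a random intercept per centre. Sensitivity is the marginal mean for a diseased patient.
- **Interval:** "Twosided 95%-logit confidence intervals with p-values are reported".
- **Decision:** "The first primary null hypothesis can be rejected if the lower limit of both confidence intervals lies above the according pre-defined minimum threshold", that is 0.80 for sensitivity and 0.65 for specificity.
- **Fallback, only if the model does not converge:** "separate estimates of sensitivity and specificity, respectively, are calculated for each centre and finally weighted averaged", again with a logit interval.

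Section 12.2 assumes sensitivity 99%, prevalence 1.5% and 1,470 patients, hence 22 bleeds. It states 86% power for sensitivity and an aimed overall power of 80%. On the error level it says "The two-sided significance level is set to 5% for the endpoint considering sensitivity and the endpoint considering specificity, respectively". Section 5 expects "about 50 clinical sites participating". Section 12.1.2 leaves further details to the SAP.

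**The concern.** A logit (Wald-type) interval behaves badly when nearly every case is detected, and that is what the protocol expects. If all bleeds are detected, the estimated log-odds has no finite maximum and the interval carries no information. If one is missed, the standard error on the logit scale is about 1, which is very wide with 22 cases.

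Sensitivity is one of two co-primary endpoints that must both succeed, and EP2 (the AUC of the three-level system) is confirmatory only if they do. A device that detected every bleed could therefore fail the primary endpoint, or get an answer that depends on where an optimiser stopped, and EP2 would fall with it.

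**Working it through.** **Inputs.** From section 12.2: true sensitivity p1 = 0.99, minimum p0 = 0.80, two-sided 5%, N = 1,470, prevalence 0.015. Expected bleeds: 1,470 × 0.015 = 22.05. From section 5: about 50 centres.

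**1. The stated 86%.** One-sample normal approximation with the null variance in the critical value:

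power = Φ{[√n(p1 − p0) − 1.96√(p0(1 − p0))] / √(p1(1 − p1))}

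With n = 22: [4.690 × 0.19 − 1.96 × 0.40] / 0.0995 = 0.107 / 0.0995 = 1.08, so power = 85.9%. The figure reproduces, but for a test that 12.1.2 does not use.

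**2. The rule in 12.1.2, no centre variance.** For x of n detected, the lower limit is expit{ln(x/(n − x)) − 1.96√(1/x + 1/(n − x))}.

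| Result | Probability at 99% | Logit lower limit |
|---|---|---|
| 22/22 | 0.99^22 = 80.2% | no finite interval |
| 21/22 | 17.8% | ln 21 = 3.045, SE 1.024, giving 73.9% |
| 20/22 | 20/22 or fewer: 2.0% | 70.0% |

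Nothing passes at 22 bleeds. The best finite result with up to 30 bleeds is 29/30, at 79.8%. One miss first clears the threshold at 30/31 (80.4%), and P(31 or more bleeds) under Binomial(1470, 0.015) is 4.0%. Averaged over that distribution, power is about 1.0%.

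**3. With centre variance.** The protocol gives no centre SD, so a range is assumed. In simulated fits of the planned model (50 centres, 1,470 patients, 22 bleeds, 40 fits per setting, limit for an average centre), 22/22 gave standard errors in the hundreds and a lower limit of about 0 every time. At 21/22:

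| Assumed SD | Median lower limit | Share above 80% |
|---|---|---|
| 0 | 73.9% | 0% |
| 0.5 | 74.6% | 0% |
| 1.0 | 78.5% | 22.5% |
| 1.5 | 82.7% | 80% |

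Since 21/22 occurs in 17.8% of such trials, the gain is 0.225 × 17.8 = 4 points at SD 1.0 and 0.80 × 17.8 = 14 points at SD 1.5.

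A separate set of 250 lme4 fits per setting declared success in 10%, 9% and 6% of trials at SD 0, 0.5 and 1. At SD 0 and 0.5 nearly all of these came from arbitrary standard errors at 22/22. Convergence was reported in at least 98.8% of fits. The two sets differ at 22/22, which shows that the answer there depends on the software.

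**4. The fallback.** With 22 bleeds spread evenly at random over 50 centres, the expected number of centres without a bleed is 50 × (49/50)^22 = 32, and only about 3.5 have two or more. At 22/22 every centre with a bleed has sensitivity 1 and no variance, so the logit interval is undefined again.

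**5. Alternatives at 22 bleeds.**

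| Interval | 22/22 | 21/22 |
|---|---|---|
| Clopper-Pearson | 0.025^(1/22) = 84.6% | 77.2% |
| Wilson | 85.1% | 78.2% |

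Either passes only at 22/22: power 80.2%, one-sided error 0.8^22 = 0.74%. Clopper-Pearson cannot pass with 16 or fewer bleeds (0.025^(1/16) = 79.4%). Weighting its power at each bleed count by Binomial(1470, 0.015) gives about 75%.

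**The case against.** **The SAP may settle it.** Handling of complete separation, such as a correction or penalised fitting, is often left to the SAP, which is not at hand. But the interval type and decision rule are already set in the protocol. Adding 0.5 at 22/22 gives ln 45 − 1.96 × √(1/22.5 + 1/0.5) = 3.807 − 2.802 = 1.004, a lower limit of 73.2%, so a correction inside the logit interval does not rescue it.

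**A reader might infer that the rule can never be met.** That is too strong. The zero is strict only with little centre variance, and large variance or arbitrary standard errors produce some successes.

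**A reader might infer that the by-centre fallback cannot be computed at all.** The protocol does not support that. It does not state the weights or the treatment of centres without a bleed, and with a miss an average over the centres that have bleeds could be formed. Failure is shown only when every bleed is detected. Whether the fallback is triggered also depends on how non-convergence is defined. If separation counted as non-convergence, the fallback would be used and would meet the same undefined interval.

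**Blinded re-estimation may repair it.** Section 12.3 re-estimates N from prevalence with the same sample size method, so the mismatch stays.

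**A reader might infer that an exact interval restores 80% power at no cost.** It does so only at exactly 22 bleeds. In addition, 12.1.2 counts missing or inconclusive results as wrong, and under the exact rule one such case among 22 bleeds fails the trial.

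**Conclusion.** The concern stands. The test in 12.1.2 is not the test powered in 12.2. Under the protocol's own assumptions the logit rule has zero power at exactly 22 bleeds and about 1% averaged over random event counts, against 86% stated. This assumes no centre variance and a plain logit interval. With an assumed random-intercept SD of 1.0 to 1.5 the simulations add roughly 4 to 14 points, which does not change the conclusion. In the most likely outcome, all bleeds detected, neither the model nor the fallback gives a valid interval. This needs correcting before the data are analysed, because changing the interval once results are known would undermine the confirmatory claim.

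**What to change.** - **Section 12.1.2:** base the sensitivity decision on a pooled Clopper-Pearson or Wilson two-sided 95% interval over all bleeds in the full analysis set. Keep the random-intercept model as a supportive analysis of centre heterogeneity. Do not let the by-centre average decide sensitivity.
- **Section 12.2:** restate the sensitivity power for the chosen rule. With Clopper-Pearson it is 80.2% at exactly 22 bleeds and about 75% averaged over random event counts at 1,470 patients, instead of 86%. Apply the same rule in the re-estimation of section 12.3.

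**Cost.** The change is to wording and calculation; no new data are collected. Centre clustering is no longer modelled in the decision, a small loss at 22/50 = about 0.4 bleeds per centre. The stated power becomes less favourable. With about 75% against the aimed 80%, the sponsor must either accept the shortfall or secure enough bleeds, which may mean more than 1,470 patients.
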